## 3. STUDY DESIGN

### 3.1 Study Design

This is a prospective, randomized, sham-controlled, multi-center investigation designed for comparison of two parallel groups, gammaCore®-R (active treatment) and a sham (inactive) treatment. The study period will begin with a four week run-in period, during which there is no investigational treatment. The purpose of the run-in period will be to establish the baseline for comparisons. The run-in period will be followed by a 12 week randomized period when the subjects will be randomized (1:1) to either active treatment or sham (inactive) treatment. Figure 1 graphically displays the study design.

The randomized period will be followed by a 24 week open label period, where the subjects in the sham treatment group will switch treatment assignment and receive a gammaCore®-R device and the gammaCore®-R group will continue to receive an active treatment (See Protocol Section 7.1 for details).

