### 3.5 Sample Size

Table 1 provides the required sample size per treatment group when the number of migraine days per 28-day period is used as the primary outcome measure. Sample size calculations are based on the clinically meaningful difference between active and sham treatment groups in change from baseline. Assuming a type I error of 5% (two-sided) and 90% power, Table 1 displays the required sample sizes for different values of the common standard deviation (2.0, 2.5, 3.0 and 3.5) and the presumed difference between treatment groups (1, 1.5 and 2 days). Selecting an improvement of 1 day and a common standard deviation of 2.5 requires 133 subjects per treatment group. With 15% drop-out during the randomized treatment period, a total of 160 subjects per treatment group (or 320 subjects total) would need to be randomized.

**Table 1: Required Sample Size per Treatment Group  
Assuming Type I Error ( $\alpha$ ) = 5% (two-sided) and 90% Power**

Variability (Common SD*, $\sigma$ )	Clinically Significant Improvement: Active – Sham = $\Delta$		
	1-day	1.5-day	2-day
2.0	86	--	--
2.5	133	60	34
3.0	191	86	49
3.5	259	115	66

\*Estimated standard deviation for change from baseline. Standard deviations for baseline and post treatment scores are between 2.0 to 3.5.

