4. If number of study days in the DB period is greater than or equal to 70, but less than 84, the month 3 value would be calculated as:

$$\text{Month 3 Value} = \sum_{i=1}^z \text{Day } i, \text{ where Day } i = 1 \text{ (had a migraine)}$$

where  $z$  represents the subject's last day of participation with diary data present.

To ensure consistency of this value for all subjects, the value will be adjusted to reflect an estimated number of days with migraine per 28 day interval. For example, if a subject records data for  $x$  days out of 28 days and have  $y$  days with migraine, then the adjusted number of days with migraine in 28 days is  $(28/x)*y$ , with a maximum value of 28.

Then the change from Run-in is calculated using the adjusted values as:

$$\text{Change}_{\text{Run-in}} = \text{Month 3 value} - \text{Run-In value}$$

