#### 7.4.2 Secondary Endpoints

##### *Percentage Reduction in Migraine Days and Responder Rate*

The percentage reduction in migraine days from the run-in period and achievement of 50% reduction in migraine days during the last 4 weeks of the randomized period are two secondary endpoints. Percentage reduction in migraine days is calculated as:

$$\text{Percentage Reduction} = -100 \times (\text{Change}_{\text{Run-in}} / \text{Run-in Value})$$

Using this value, an indicator of achievement of 50% reduction during the last 4 weeks of the randomized period can be defined as:

Response = 1 (Yes) if Percentage Reduction  $\geq 50\%$

Response = 0 (No) if Percentage Reduction is non-missing and  $< 50\%$

The number of migraine days, the change from run-in, and the percentage change from run-in to the open-label period will also be calculated. This will be completed for Month 3 and Month 6 of the OL period. For

$$\text{Month 3 OL Value} = \sum_{i=1}^{84} \text{Day } i, \text{ where Day } i = 1 \text{ (had a migraine)}$$

In the event that a subject does not have at least 70 days in the OL period the following rules will be used to calculate the Month 3 OL value:

1. If the number of study days in the OL period is less than 70, the month 3 OL value will not be calculated, but rather imputed to the DB value (and thus resulting in a  $\text{Change}_{\text{OL3}} = \text{Change}_{\text{Run-in}}$ , implying no change between the 3 month DB and 3 month OL periods).

$$\text{Month 3 OL Value} = \text{Month 3 (DB) Value}$$

2. If number of study days in the OL period is greater than or equal to 70, but less than 84, the month 3 OL value would be calculated as:

$$\text{Month 3 OL Value} = \sum_{i=1}^z \text{Day } i, \text{ where Day } i = 1 \text{ (had a migraine)}$$

where  $z$  represents the subject's last day (within 84 days) of participation in the OL period with diary data present.

To ensure consistency of this value for all subjects, the value will be adjusted to reflect an estimated number of days with migraine per 28 day interval. For example, if a subject records data for  $x$  days out of 28 days and have  $y$  days with migraine, then the adjusted number of days with migraine in 28 days is  $(28/x)*y$ , with a maximum value of 28.

Then the change from Run-in is calculated using the adjusted values as:

$$\text{Change}_{\text{OL3}} = \text{Month 3 OL value} - \text{Run-In value}$$

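### Rule 4 of the primary endpoint does not limit its last summed day to the double-blind period, so read literally it lets open-label days into the Month 3 value of on-schedule early completers

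*SAP*

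**What the plan says.** SAP section 7.4.1 defines the primary endpoint as the change from run-in to Month 3, the final four weeks of the randomized period. With a full double-blind period, the Month 3 value sums Days 57 to 84. Rule 4 covers shorter periods: "If number of study days in the DB period is greater than or equal to 70, but less than 84". It sums from i=1 to z, where z "represents the subject's last day of participation with diary data present", and rescales the result to 28 days.

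The other definitions of z are bounded. In the same section, the run-in z is limited to the run-in period. In section 7.4.2, the open-label Month 3 z "represents the subject's last day (within 84 days) of participation in the OL period with diary data present", and the open-label Month 6 z is limited to 168 days and to the open-label period.

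Three other parts of the SAP matter here:
- Table 2 places Visit 6 at Day 84 with a window of 5 days either side, and continues the diary to Visit 12 (nominal Day 252).
- Section 3.1 states that after the randomized period "the subjects in the sham treatment group will switch treatment assignment and receive a gammaCore®-R device".
- Section 3.4 places the primary analysis after all subjects have finished the randomized period but before the open-label period formally ends.

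**The concern.** A subject whose Visit 6 falls on Days 79 to 83 is a compliant completer with fewer than 84 double-blind days, so rule 4 applies. That subject's last day of participation with diary data is normally an open-label day. Section 6.1 keeps a study-day count relative to randomization during the open-label period, so Day i is defined after the switch and a program can sum it.

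If the rule is programmed as written, sham subjects contribute active-device days to the primary value and the contrast is no longer sham against active. The value would also depend on the data cut, because z moves later as open-label diary days accumulate. The problem carries over to percentage reduction and responder status, to headache and acute-medication days (derived in the same way, section 7.4.2), and to the changes from double-blind to open-label. The missing-data sensitivity analyses in section 8.4.1 target imputed points. They may not detect it, because a rule 4 value is summed and rescaled.

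**Working it through.** **1. The plan's own sample size.** Section 3.5 fixes the error rates: "Assuming a type I error of 5% (two-sided) and 90% power". For the chosen effect and SD it then states: "Selecting an improvement of 1 day and a common standard deviation of 2.5 requires 133 subjects per treatment group". To allow for a 15% loss it raises this to 160 per arm. Section 3.1 gives the allocation: "randomized (1:1) to either active treatment or sham (inactive) treatment".
- Normal approximation: n = 2(1.960 + 1.282)² × 2.5² / 1² = 131.3, so 132 per arm. The exact t version gives 133, as stated.
- Drop-out: 133/0.85 = 156.5, so 157; the stated 160 is slightly more.
- Power at 133 per arm for a 1-day difference is 90.4% (normal) or 90.1% (t).

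The sample size is sound. It serves below only as the reference point.

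**2. Who can be affected.**
- Left the study on Days 70 to 83: rule 4 applies, but there are no later days. Not affected.
- 84 or more double-blind days: Days 57 to 84 are used. Not affected.
- Visit 6 on Days 79 to 83 and continued: rule 4 applies and open-label diary days exist. Affected.

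Days 79 to 83 are 5 of the 11 permitted days (5/11 = 45%). That would be the affected share only if visits were spread evenly over the window, which is an assumption. The SAP gives no count.

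**3. Open-label share s of the summed days, from i=1 as rule 4 is written.**
- Visit 6 on Day 80, diary to Day 252: (252 − 80)/252 = 172/252 = 68%.
- Visit 6 on Day 79 plus 168 open-label days: 168/247 = 68%.
- Visit 6 on Day 79 plus 84 open-label days, as might be the case at the primary analysis: 84/163 = 52%.
- z capped at Day 84, Visit 6 on Day 80: 4/84 = 4.8%. With Visit 6 on Day 79: 5/84 = 6.0%.

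**4. Effect on the comparison.** Let f be the share of sham subjects affected (not in the SAP; assumed 5% to 50%). Assume the full 1-day benefit on every open-label day, SD 2.5 and 133 per arm. The diluted difference is 1 − f × s.

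| f | s = 0.68: difference, power | s = 0.52: difference, power | s = 0.06 (z capped at Day 84): difference, power |
|---|---|---|---|
| 5% | 0.97, 88% | 0.97, 89% | 1.00, 90% |
| 10% | 0.93, 86% | 0.95, 87% | 0.99, 90% |
| 25% | 0.83, 77% | 0.87, 81% | 0.99, 90% |
| 50% | 0.66, 58% | 0.74, 68% | 0.97, 89% |

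One-subject illustration, with assumed rates of 6 migraine days per 28 on sham and 5 on active: blinded days alone give 6.0. Days 1 to 247 with the switch after Day 79 give (79 × 6 + 168 × 5)/247 = 5.3.

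**5. The lower limit.** Suppose z is bounded at Day 80. The sum from i=1 still includes 56 days before Month 3, and 56/80 = 70% of the days summed. Bounding z removes the open-label days but leaves an average over Days 1 to z. The 70-day threshold itself fits a Day 57 start, since 70 − 56 = 14 days, half of Month 3.

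**The case against.** The strongest answer is that context already confines the value to blinded days. Sections 2.1 and 7.4.1 place the endpoint in the randomized period, and rule 4's own trigger counts days in the double-blind period. Section 7.4.2 contrasts the result with the open-label values. The rescaling text speaks of x days out of 28, which does not suit a sum running to Day 252. This stands as evidence of intent. A reader might infer that the plan deliberately ends the window outside the blinded period; the SAP does not support that. What it contains is an omitted qualifier in the operative formula, in conflict with the endpoint definition. The objection does not remove the problem, because a programmer following the formula and one following the definition would produce different primary values.

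It is also fair to say that the size is easily overstated. The 68% needs near-complete open-label follow-up and a strictly literal program, and many subjects will have fewer open-label days at the primary analysis. A reader might put the share under a Day 84 cap at 4/28 = 14%, but that assumes a Day 57 start, which rule 4 does not have. As written it is 4/84, about 5%. Nor is a false positive the expected result: when only the sham arm changes device, the arms are drawn together. Open-label expectation could shift both arms, so the direction is expected rather than certain.

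Finally, the start at i=1 is the larger fault in the same formula, since it affects every rule 4 subject in both arms. That is correct, and it is a reason to repair both limits together.

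**Conclusion.** The point holds as a conflict between the endpoint definition and the formula that implements it. Rule 4's z has no double-blind limit and, read literally, admits open-label days for completers whose Visit 6 falls on Days 79 to 83. The number of such subjects is not given, so the size of the effect is unknown. Taken literally, with open-label days at about 68% of the sum, power would fall from about 90% to between 88% and 58% as the affected share of sham subjects rises from 5% to 50%. With z capped at Day 84 it would stay at about 89% to 90%. These figures rest on the assumed shares and on a full 1-day benefit on every open-label day. The planned sample size is unaffected. The wording should be settled before unblinding, because it fixes the primary value of subjects who followed the schedule.

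**What to change.** In rule 4, define z as the last diary day in the double-blind period, before the open-label device is issued and no later than Day 84. Add that no diary day on or after issuance enters any double-blind value, and apply the same limit to headache days and acute-medication days.

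In the same edit, replace the lower limit i=1 so that the value covers the final four weeks of the randomized period. State exactly which days are summed and which x is used in the 28/x rescaling. State also whether the issuance date counts as a double-blind day, since this decides whether a Visit 6 on Day 84 falls under rule 4.

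The cost is a short SAP amendment and a date filter on dates already recorded. No new data are needed and the sample size does not change.

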#### 7.4.2 Secondary Endpoints

##### *Percentage Reduction in Migraine Days and Responder Rate*

The percentage reduction in migraine days from the run-in period and achievement of 50% reduction in migraine days during the last 4 weeks of the randomized period are two secondary endpoints. Percentage reduction in migraine days is calculated as:

$$\text{Percentage Reduction} = -100 \times (\text{Change}_{\text{Run-in}} / \text{Run-in Value})$$

Using this value, an indicator of achievement of 50% reduction during the last 4 weeks of the randomized period can be defined as:

Response = 1 (Yes) if Percentage Reduction  $\geq 50\%$

Response = 0 (No) if Percentage Reduction is non-missing and  $< 50\%$

The number of migraine days, the change from run-in, and the percentage change from run-in to the open-label period will also be calculated. This will be completed for Month 3 and Month 6 of the OL period. For

$$\text{Month 3 OL Value} = \sum_{i=1}^{84} \text{Day } i, \text{ where Day } i = 1 \text{ (had a migraine)}$$

In the event that a subject does not have at least 70 days in the OL period the following rules will be used to calculate the Month 3 OL value:

1. If the number of study days in the OL period is less than 70, the month 3 OL value will not be calculated, but rather imputed to the DB value (and thus resulting in a  $\text{Change}_{\text{OL3}} = \text{Change}_{\text{Run-in}}$ , implying no change between the 3 month DB and 3 month OL periods).

$$\text{Month 3 OL Value} = \text{Month 3 (DB) Value}$$

2. If number of study days in the OL period is greater than or equal to 70, but less than 84, the month 3 OL value would be calculated as:

$$\text{Month 3 OL Value} = \sum_{i=1}^z \text{Day } i, \text{ where Day } i = 1 \text{ (had a migraine)}$$

where  $z$  represents the subject's last day (within 84 days) of participation in the OL period with diary data present.

To ensure consistency of this value for all subjects, the value will be adjusted to reflect an estimated number of days with migraine per 28 day interval. For example, if a subject records data for  $x$  days out of 28 days and have  $y$  days with migraine, then the adjusted number of days with migraine in 28 days is  $(28/x)*y$ , with a maximum value of 28.

Then the change from Run-in is calculated using the adjusted values as:

$$\text{Change}_{\text{OL3}} = \text{Month 3 OL value} - \text{Run-In value}$$

$$\text{Month 6 OL Value} = \sum_{i=141}^{168} \text{Day } i, \text{ where Day } i = 1 \text{ (had a migraine)}$$

In the event that a subject does not have at least 154 days in the OL period the following rules will be used to calculate the Month 6 value:

1. If the number of study days in the OL period is less than 154, the month 6 OL value will not be calculated, but rather imputed to the Month 3 OL value (and thus resulting in a  $\text{Change}_{\text{OL6}} = \text{Change}_{\text{OL3}}$ , implying no change between the 6 month OL and 3 month OL periods).

$$\text{Month 6 OL Value} = \text{Month 3 OL Value}$$

2. If number of study days in the OL period is greater than or equal to 154, but less than 168, the month 6 OL value would be calculated as:

$$\text{Month 6 OL Value} = \sum_{i=1}^z \text{Day } i, \text{ where Day } i = 1 \text{ (had a migraine)}$$

where  $z$  represents the subject's last day of participation (within 168 days) in the OL period with diary data present.

To ensure consistency of this value for all subjects, the value will be adjusted to reflect an estimated number of days with migraine per 28 day interval. For example, if a subject records data for  $x$  days out of 28 days and have  $y$  days with migraine, then the adjusted number of days with migraine in 28 days is  $(28/x)*y$ , with a maximum value of 28.

Then the change from Run-in is calculated using the adjusted values as:

$$\text{Change}_{\text{OL6}} = \text{Month 6 OL value} - \text{Run-In value}$$

Results will be stratified by randomized treatment group.

In addition, the change from the double-blind period to 3 and 6 months of the open label period will be calculated or derived in the same manner for the comparison of the run-in to double-blind, randomized phase. Results will be stratified by randomized treatment group. For the calculation of percent change from the double-blind period to each of the open label periods, if there were zero migraine days at the double-blind period, percent reduction will be imputed as 100%.

$$\text{Change}_{\text{OL3DB}} = \text{Month 3 OL value} - \text{Month 3 value}$$

$$\text{Change}_{\text{OL6DB}} = \text{Month 6 OL value} - \text{Month 3 value}$$

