### 2.2 Secondary Objectives

The secondary objectives are:

- To evaluate the rate of responders for the gammaCore®-R group compared to the sham group. A responder is defined as recording at least 50% reduction in migraine days during the last four weeks in the twelve-week randomization period compared to the four week run-in period.
- To evaluate the difference between the gammaCore®-R and sham treatment groups in mean reduction in number of headache days during the last four weeks in the twelve-week randomized period compared to the four week run-in period.
- To evaluate the difference between the gammaCore®-R and the sham treatment groups in the mean reduction in acute headache medications taken during the last four weeks in the twelve-week randomized period compared to the four week run-in period.
- Compare improvement in headache disability using Headache Impact Test-6 (HIT-6)
- Compare improvement in Migraine Disability Assessment (MIDAS)
- Compare Quality of Life EQ-5D-5L
- Reduction of number of headache/migraine days in the open label period compared to baseline run-in period and the randomized period

- Adverse events

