**Figure 1: Diagram of Study Design**

### 3.2 Randomization

Subjects will be randomized to either the active treatment arm or sham control arm (allocation 1:1) under a randomized variable block design, stratified by study site.

Subjects will be randomized using Merge eClinical OS Interactive Web Response system (IWRS) via computer key board data entry for a web based interface.

The site personnel (the investigator or his designee) will enter the required study and subject information and will then be provided with a subject randomization number and device serial number. Once subject numbers, serial numbers, and randomization numbers have been assigned, they cannot be reassigned.

The IWRS will provide the site personnel confirmation of the randomization number and device serial number assigned to each subject.

A sponsor designee will also have a copy of the randomization schemes for each study site and will be responsible for providing the un-blinded trainer with the randomization schemes.

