### 5.1 Intent-to-Treat (ITT) Population

The Intention to treat (ITT) population includes all randomized subjects with at least one verified treatment post-training during the 12 week randomized period. The ITT population will be analyzed using the subject's randomized treatment regardless of which treatment the subject actually received.

The ITT is considered the primary analysis dataset, and will be used for all primary and secondary efficacy analyses.

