## 7.4 Efficacy

### 7.4.1 Primary Endpoint

The primary endpoint is the change from run-in to the last four weeks (Month 3) of the randomized period in the number of migraine days.

The diary data will collect for each day an indicator (1=Yes, 0=No, or missing) of whether the subject experienced a migraine. One 24 hour period per migraine will be designated as a migraine day.

The visit level value for a given subject is then the sum of the daily diary day indicators of whether the subject experienced a migraine which gives the number of days with a migraine. Calculations are as follows:

$$\text{Run-in Value} = \sum_{i=-z-28}^{-z} \text{Day } i, \text{ where Day } i = 1 \text{ (had a migraine)}$$

where  $z$  represents the subject's last day with diary data during the run-in period.

In the event that a subject does not 28 diary days in the run-in period the following rules will be used to calculate the run-in value:

1. If the number of diary days in the run-in period is less than 21, the run-in value will not be calculated, and will be considered missing.
2. If number of diary days in the run-in period is greater than or equal to 21, but less than 28, the run-in value would be calculated as:

$$\text{Run-in Value} = \sum_{i=-z-x}^{-z} \text{Day } i, \text{ where Day } i = 1 \text{ (had a migraine)}$$

where  $z$  represents the subject's last day with diary data during the run-in period, and  $x$  is the number of days with diary data during the run-in period.

To ensure consistency of the run-in value for all subjects, the value will be adjusted to reflect an estimated number of days with migraine per 28 day interval. For example, if a subject records data for  $x$  days out of 28 days and have  $y$  days with migraine, then the adjusted number of days with migraine in 28 days is  $(28/x)*y$ , with a maximum value of 28.

$$\text{Month 3 Value} = \sum_{i=57}^{84} \text{Day } i, \text{ where Day } i = 1 \text{ (had a migraine)}$$

In the event that a subject does not have at least 84 study days in the DB period the following rules will be used to calculate the Month 3 value:

3. If the number of study days in the DB period is less than 70, the month 3 value will not be calculated, but rather imputed to the run-in value (and thus resulting in a  $\text{Change}_{\text{Run-in}}=0$ , implying no change between periods).

Month 3 Value =Run-in Value

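### Open-label migraine-day values are filled from the blinded or run-in period, so the open-label-minus-blinded change is shrunk and its confidence interval is too narrow

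*SAP*

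**What the plan says.** Three rules in the SAP link together.

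- **Blinded Month 3 (section 7.4.1).** With fewer than 70 days in the blinded period, "the month 3 value will not be calculated, but rather imputed to the run-in value".
- **Open-label Month 3 (section 7.4.2).** With fewer than 70 open-label days, "the month 3 OL value will not be calculated, but rather imputed to the DB value". The SAP states the consequence itself: "implying no change between the 3 month DB and 3 month OL periods".
- **Open-label Month 6 (section 7.4.2).** With fewer than 154 open-label days, "the month 6 OL value will not be calculated, but rather imputed to the Month 3 OL value".

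Section 5.1 says that the ITT population "will be used for all primary and secondary efficacy analyses". Section 3.1 says that at the start of the open-label period "the subjects in the sham treatment group will switch treatment assignment and receive a gammaCore®-R device". The objective served by these values is in section 2.2: "Reduction of number of headache/migraine days in the open label period compared to baseline run-in period and the randomized period".

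Section 8.4.2 plans two-sided 95% confidence intervals for secondary outcomes, including the open-label time points. For change from the end of the blinded period, section 7.4.2 says that it will be calculated, while section 8.4.2 says only that summaries may be produced.

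**The concern.** The objective asks how migraine days in the open-label period differ from run-in and from the randomized period. For a subject without enough open-label diary days, the rule supplies the answer to the second comparison in advance: no difference. In the ex-sham arm a result obtained on sham is then reported as a result on the active device. A subject who left the blinded period early has run-in, blinded, open-label Month 3 and open-label Month 6 values that are all equal, although that subject was never in the open-label period.

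The filled values then enter the means and intervals as if they had been observed. The planned safeguards do not reach them. The multiple imputation and pattern-mixture analyses in section 8.4.1 are limited to values imputed under section 7.4.1, and the complete-population analysis in section 8.4.3.5 covers only run-in and blinded data. Section 8.1 adds an imputation flag to the dataset but no correction to the variance.

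**Working it through.** **Inputs from SAP section 3.5:** difference of 1 day, SD 2.5 for change from baseline, two-sided 5%, 90% power, 133 per group, 15% dropout in the randomized period, 160 per group.

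**Assumptions (not in the SAP):**
- a further loss g of 0, 10 or 20% of blinded completers before open-label Day 70;
- SD s = 2.5 also for the open-label-minus-blinded change;
- a true change d = 1 day after switching;
- dropout unrelated to outcome.

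**1. The plan's own figure.** The normal approximation gives 132 per group and the exact noncentral t gives 133, as stated. 133/0.85 = 156.5, so 157; the plan's 160 is slightly above this. 160 × 0.85 = 136 per group are expected to finish the blinded period.

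**2. Tracing the rules.**

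| Subject | Blinded Month 3 | OL Month 3 | OL Month 6 | OL minus blinded, Month 3 / Month 6 |
|---|---|---|---|---|
| Fewer than 70 blinded days | run-in value | run-in value | run-in value | 0 / 0 |
| 70 or more blinded days, fewer than 70 OL days (including none) | calculated | blinded value | blinded value | 0 / 0 |
| 70 to 153 OL days | calculated | calculated from OL diary | OL Month 3 value | calculated / calculated from OL Month 3 |
| 154 or more OL days | calculated | calculated from OL diary | calculated from OL diary | calculated / calculated |

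The zeros are for absolute change. Section 7.4.2 sets percent reduction to 100% when the blinded value is zero.

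**3. Share set to zero.** m = 1 − 0.85(1 − g). For g = 0, 0.10 and 0.20, m = 0.15, 0.235 and 0.32. For this contrast it does not matter when in the blinded period a subject left.

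**4. Mean and standard error, n = 160 in one arm.**
- Reported mean = (1 − m)d.
- SE as planned = √{[(1 − m)s² + m(1 − m)d²]/160}.
- SE from observed subjects = s/√[160(1 − m)].

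| m | Reported change | SE as planned | SE from observed data | Ratio | t as planned | t observed |
|---|---|---|---|---|---|---|
| 0.15 | 0.85 | 0.184 | 0.214 | 0.86 | 4.6 | 4.7 |
| 0.235 | 0.77 | 0.176 | 0.226 | 0.78 | 4.3 | 4.4 |
| 0.32 | 0.68 | 0.167 | 0.240 | 0.70 | 4.1 | 4.2 |

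The standard error is thus about 14, 22 and 30% too small. The t statistic hardly moves, because estimate and standard error shrink together.

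**5. Coverage.** A simulation of the ex-sham arm (4000 runs, changes from run-in with SD 2.5 and an assumed correlation of 0.5 between periods) gave coverage of the nominal 95% interval for this contrast of about 87, 74 and 52% at the three values of m.

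**6. Change from run-in.** Here the direction varies.
- Ex-sham arm, assumed true changes −1 (blinded) and −2 (open-label), all 15% lost before Day 70, no open-label loss: 0.85 × (−2) = −1.70.
- The same with 20% open-label loss: 0.15 × 0 + 0.17 × (−1) + 0.68 × (−2) = −1.53, against −2.
- Active arm with a waning effect, −2 then −1, no blinded loss, 15% open-label loss: 0.85 × (−1) + 0.15 × (−2) = −1.15, so the open-label benefit is overstated.
- Active arm with a steady −2 and open-label loss only: the mean is unbiased.

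**The case against.** The strongest defence is that the rule is open about its assumption, that imputed values are flagged, that open-label results are shown by randomized group so that sham carry-over stays in the ex-sham arm, and that the primary test is untouched. Assuming no change may also be more cautious than analysing only those who stay, because non-responders may leave an uncontrolled phase. All of this stands, and it limits both the weight of the point and the remedy. It does not make a sham-period or run-in value an open-label observation, and it does not repair the interval.

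A reader might infer more than the SAP supports:

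- **That every imputed value gives a zero change from the blinded period.** A subject with 70 to 153 open-label days carries a genuine open-label Month 3 value to Month 6.
- **That all open-label changes are pulled toward zero.** A blinded completer lost in the open-label period receives the blinded change from run-in, which need not be zero and can overstate benefit.
- **That the narrow interval creates false claims of benefit.** For the open-label-minus-blinded contrast the t statistic is nearly unchanged.
- **That 24 to 32% imputed is the plan's figure.** Only the 15% is; the SAP gives no open-label loss rate.

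The SAP also never says outright that subjects who did not enter the open-label period receive open-label values. This follows from the ITT rule with the fewer-than-70-days condition, since section 6.4 counts open-label days from device issuance.

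**Conclusion.** The concern holds for secondary open-label outcomes. Anyone with fewer than 70 open-label days has an absolute open-label-minus-blinded change fixed at 0 at Months 3 and 6, so the reported mean is exactly (1 − m) times the mean among the remaining subjects. Treating the latter as the true value requires dropout unrelated to outcome. The consequence is a biased estimate with a falsely narrow interval. The size is 85% of the true change at the plan's own 15% dropout, and 77 to 68% under the assumed further loss of 10 to 20%. The standard-error figures also rest on SD 2.5 for this contrast and a true change of 1 day. For change from run-in, the direction of bias depends on the arm and on when the subject left. No planned sensitivity analysis covers these values. The SAP should be changed, but the primary conclusion does not depend on it.

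**What to change.** In section 7.4.2 and the matching parts of sections 5 and 8.4.2:

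1. Define an open-label analysis set of subjects who received the open-label device.
2. Do not fill open-label values from the blinded or run-in period.
3. Report open-label Month 3 and Month 6 from observed open-label diary data with n shown. Alternatively, use a mixed model or multiple imputation with all available blinded and open-label months and treatment period in the model. Imputing only from a subject's own open-label months would fail for those who have none.
4. Keep the carried-forward, no-change rule as a labelled sensitivity analysis and show it beside the main result.

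The cost is SAP wording and revised derivations; no new data are needed. There are two drawbacks. The n will differ by month, and observed-only results condition on staying in the open-label period, so they could overstate benefit if non-responders leave. That is why the two analyses should be shown together.
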